10.4 Study Drug Administration Modification

Clinical judgment will be used to determine appropriate management of the subject during any AE. The criteria for dose modification for drug-related AEs (excluding hypertension and

skin toxicity) are summarized in Table 4. Further management is at the discretion of the investigator, who may discuss this with the medical monitor if necessary.

Table 4: Dose Modification Guidelines for Drug-Related Adverse Events

Drug-Related Adverse Events (excluding Hypertension¹ and Skin Toxicity²)	Intervention
Grade 1	Continue treatment at same dose
Grade 2	Continue treatment at same dose
Grade 3	Decrease dose (see Section 10.4.2 for tivozanib and Section 10.4.3 for sorafenib dose reduction guidelines)
Grade 4	Interrupt dosing; restart at lower dose as soon as toxicity improves to \leq Grade 2 (see Section 10.4.1 for tivozanib and Section 10.4.3 for sorafenib dose reduction guidelines)

¹ Hypertension must be treated as described in Section 10.4.1 prior to dose modification

² Skin toxicity should be managed as described in [Section 10.2](#)

10.4.1 Tivozanib Dose Reduction

Dose reductions of tivozanib to 1.0 mg/day will be allowed for subjects with \geq Grade 3 drug-related adverse events. The exception is hypertension, which must be treated with anti-hypertensive drugs (see [Appendix D](#)) prior to dose reduction.

The dose of tivozanib may be reduced to 1.0 mg/day. Once the dose of tivozanib is reduced, it may not be re-escalated throughout the study. If a subject is unable to tolerate a dose of 1.0 mg/day due to toxicities thought to be related to tivozanib, dosing with tivozanib should be discontinued.

Any modification of study drug administration, and the reason for such action, must be clearly noted on the subject's eCRF using the Adverse Events reporting page.

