Dose reduction: 
Tivozanib: Dose reduction will be allowed for subjects with \geq Grade 3 drug-related adverse events. The exception is hypertension, which must be treated with anti-hypertensive drugs prior to dose reduction.
 
The dose of tivozanib may be reduced to 1.0 mg/day. If a subject is unable to tolerate a dose of 1.0 mg/day due to toxicities thought to be related to tivozanib, treatment should be interrupted for up to 4 weeks. Once the dose of tivozanib is reduced, it may not be re-escalated throughout the study.
 
Sorafenib: Dose reduction will be allowed for subjects with \geq Grade 3 drug-related adverse events. The dose of sorafenib will be reduced to 400 mg once daily. If toxicities do not resolve, sorafenib may be further reduced to 400 mg once every other day. If a subject is unable to tolerate a dose of 400 mg once every other day due to toxicities thought to be related to sorafenib, treatment should be interrupted. If toxicities resolve to \leq Grade 1, the dose of sorafenib may be re-escalated to the previous dose level at the discretion of the investigator.
 
Dose interruption (tivozanib and/or sorafenib):
 
Subjects with Grade 4 drug-related toxicity, or Grade 3 drug-related toxicity that is persistent despite dose reduction and appropriate medical care, should have their treatment interrupted to allow for adequate resolution of the toxicity. Tivozanib/sorafenib may be interrupted for up to 4 weeks. If a subject is able to resume treatment after interruption of \leq 4 weeks, missed doses will not be made up (ie, cycle duration will remain unchanged). If any drug-related toxicity results in interruption of $>$ 4 weeks, the subject should be discontinued from the study unless there is clear benefit from treatment, in which case the investigator must contact the medical monitor to review the subject's condition in order to resume treatment. Subjects removed from treatment for reasons other than radiological evidence of progressive disease should still be followed with regular tumor assessments until disease progression is confirmed by an independent radiology review or start of new treatment, and for survival thereafter.

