8.1 Study Drug

Prior to the start of the study, the sponsor will provide labeled supplies of tivozanib to the study center investigational pharmacy. Tivozanib is formulated for oral administration as a white opaque number 4 gelatin capsule containing 1.0 or 1.5 mg tivozanib. Sorafenib is formulated for oral administration as a round, biconvex, red film-coated tablet, debossed with the “Bayer cross” on one side and “200” on the other side.

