10.4.2 Tivozanib Dose Interruption

Subjects with Grade 4 drug-related toxicity, or Grade 3 drug-related toxicity that is persistent despite appropriate medical care, should have their dose interrupted to allow for resolution of the toxicity. Tivozanib may be interrupted for up to 4 weeks. If a subject is able to resume treatment after interruption of \leq 4 weeks, missed doses will not be made up (ie, cycle duration will remain unchanged). If any drug-related toxicity results in interruption of $>$ 4 weeks, the subject should be discontinued from the study unless there is clear benefit from treatment, in which case the investigator must contact the medical monitor to review the subject's condition in order to resume treatment. Subjects removed from treatment for reasons other than radiological evidence of progressive disease should still be followed with regular tumor assessments (see [Section 7.2.4](#)) until disease progression is confirmed by independent radiology review or start of new treatment, and for survival thereafter.

Any modification of study drug administration, and the reason for such action, must be clearly noted on the subject's eCRF using the Adverse Events reporting page).

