11.1 Criteria for Treatment Discontinuation (Stopping Rules)

Subjects will be discontinued from further treatment with study drug in the event of any of the following:

1. Death
2. Unacceptable toxicity considered by the investigator to require removal of the subject from study treatment.

Note: Adverse events resulting in a subject's permanent discontinuation from the study treatment, regardless of seriousness or relationship to study drug, MUST be promptly reported to the sponsor/designee. Subjects removed from treatment for intolerable toxicity should still be followed with regular tumor assessments (see Section 7.2.4) until disease progression or start of new treatment, and for survival thereafter.

3. Documented progressive disease according to RECIST Version 1.1 at any time during the study.
4. Subjects with radiological evidence of progressive disease per investigator/local radiology assessment should continue treatment until progressive disease is verified by an independent radiologist. Images should be submitted for independent review as soon as possible (see Imaging Manual for specific instructions). Verification of progressive disease is not required in the following circumstance:
 - Significant clinical deterioration that is indicative of progressive disease.
5. Subjects who have documented disease progression will be discontinued from study drug treatment and will continue to be followed up for survival.
6. Clinical progression (eg, symptomatic deterioration) not meeting the RECIST Version 1.1 criteria for radiological evidence of progressive disease but considered by the investigator to require removal of the subject from study. This includes subjects with significant clinical deterioration that is indicative of progressive disease. All related signs and symptoms of clinical progression must be captured in AE eCRF page, the term "progressive disease" should not be recorded as an adverse event or captured on the eCRF page.
7. Treatment interruption for > 4 weeks (ie, total duration of interruption, including the 1 week/cycle break in dosing of tivozanib), unless there is clear benefit from treatment, in which case the investigator must contact the medical monitor to review the subject's condition in order to resume treatment.
8. Requirement for a significant surgical procedure.

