Sensitivity Analysis #3 will be similar to Sensitivity Analysis #2, with the addition of discontinuation of therapy considered an event as well. Again, this analysis will be conducted using only the ITT population.

Sensitivity Analysis #4 will be conducted to assess the impact of missed or not evaluable (NE) tumor assessments. This analysis will use the IRR assessments and backdate any PD events that occur immediately after missing or NE assessments. If the PD occurs immediately after NE assessment (or series of NE assessments), the PD date will be the date of the first NE assessment preceding the PD. If the PD occurs immediately after a missed assessment (or series of missed assessments), the PD date will be the date of the first missed assessment preceding the PD. This analysis will use the ITT population.

All sensitivity analyses will use the same statistical methods as the primary analysis.

Exploratory Analysis on PFS

An exploratory analysis of PFS based on IRR will be summarized for the SAF population using the Kaplan-Meier method. This analysis will examine PFS for all subjects who were randomized and administered at least one dose of the study drug. This analysis will use the same statistical methods as the primary analysis.

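### The synopsis and section 10.4.1 give incompatible instructions for a subject who cannot tolerate tivozanib 1.0 mg/day (interrupt versus discontinue), and nothing says which prevails

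*Protocol*

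**What the plan says.** Two places in the protocol address the same situation in the same words: "If a subject is unable to tolerate a dose of 1.0 mg/day due to toxicities thought to be related to tivozanib". They then diverge.

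- **Synopsis, Dose reduction:** "treatment should be interrupted for up to 4 weeks".
- **Section 10.4.1:** "dosing with tivozanib should be discontinued".

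The related rules are these.

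- **Section 10.4.2** covers Grade 4, or persistent Grade 3, drug-related toxicity: "Tivozanib may be interrupted for up to 4 weeks", with resumption possible. It makes no exception for subjects already at 1.0 mg/day.
- **Table 4 (section 10.4)** says that after a Grade 4 event dosing is interrupted and restarted at a lower dose. For a Grade 3 tivozanib dose reduction it refers the reader to 10.4.2, which is the interruption section.
- **Section 10.4.1** also says: "Once the dose of tivozanib is reduced, it may not be re-escalated throughout the study".
- **Section 8.1** describes the supply as a "white opaque number 4 gelatin capsule containing 1.0 or 1.5 mg tivozanib".
- **Section 11.1, item 7** stops treatment once an interruption exceeds 4 weeks, unless there is clear benefit and the medical monitor has been consulted.

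In the SAP, Sensitivity Analysis #3 (section 4.7.2) repeats Sensitivity Analysis #2 "with the addition of discontinuation of therapy considered an event as well".

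**The concern.** A site with such a subject cannot follow both instructions. One is a temporary hold that leaves room to resume; the other ends dosing, with no hold first. Sites that read different parts of the protocol could manage similar subjects differently and each believe they are compliant.

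The same choice decides how the subject is classified: discontinued or interrupted. Several planned analyses depend on that. Because the conflict at the lowest dose exists for tivozanib and not for sorafenib, any resulting variation falls on the experimental arm in a comparison where tolerability is a secondary objective.

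**Working it through.** This is a comparison of texts. The point depends on no sample size, event count, power or alpha, so there is no formula and no figure in the plan to reproduce.

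**Step 1. Same trigger?** Yes. The conditional clause is word for word the same in the synopsis and in 10.4.1, so the two cannot be separated by grade, timing or type of toxicity.

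**Step 2. Could one instruction be a stage of the other?** An interruption can end in discontinuation through the 4-week limit in 10.4.2 and 11.1. But 10.4.1 contains no interruption step, and the synopsis does not call for discontinuation at this point; its own interruption paragraph provides for subjects who resume within 4 weeks. Neither text refers to the other, and no clause ranks body text above synopsis.

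**Step 3. Do neighbouring rules decide it?** Take a subject at 1.0 mg/day with a Grade 4 related event, other than hypertension or skin toxicity, that the investigator regards as intolerance:

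- synopsis: interrupt, resumption possible, dose on resumption not stated;
- 10.4.1: discontinue;
- 10.4.2: interrupt, resumption possible;
- Table 4: interrupt, then restart lower. Section 8.1 supplies nothing below 1.0 mg, and section 7.2.1 limits intake to one capsule a day.

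These are three different instructions, and the Table 4 cross-reference for Grade 3 reductions leads to the wrong type of section.

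**Step 4. Is sorafenib affected in the same way?** Not at its lowest level. The synopsis and 10.4.3 both say to interrupt when 400 mg every other day is not tolerated. This agreement covers that step only; Table 3 has separate discontinuation rules for repeated skin toxicity.

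**Step 5. Which analyses depend on the classification?**

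- **Primary PFS (Protocol 14.3.4, SAP 3.2.1):** stopping drug is neither an event nor, by itself, a reason for censoring while scans continue. There is no direct effect. An indirect path exists if a subject taken off drug starts another anti-tumor therapy, because PFS is then censored at the last prior assessment.
- **Sensitivity Analysis #3:** the subject has an event on discontinuation under 10.4.1, but not at that moment under the synopsis.
- **Adverse event tables (SAP 4.8.2):** withdrawal and interruption are separated by the recorded action on study drug, so the same toxicity can enter either table.
- **Exposure and relative dose intensity (SAP 4.6, 4.8.1):** duration runs from first to last dose, and missed doses are not made up, so a hold with resumption and a stop give different values.
- **Per-protocol set (Protocol 14.3.1, SAP 4.4):** two cycles, or 8 weeks, are required. The protocol's exception covers death and progression only; the SAP has none. This matters only if toxicity, reduction and failure at 1.0 mg/day all fall within the first 8 weeks.

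**Step 6. How many subjects?** The documents give no proportion failing 1.0 mg/day, so the number cannot be computed.

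**The case against.** The best case on the other side has five parts.

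**The instructions are not opposites.** This stands. An interruption may end in discontinuation, and the synopsis itself says that unacceptable toxicity leads to discontinuation. However, section 11.1 leaves what is unacceptable to the investigator's judgment and does not equate it with intolerance of 1.0 mg/day. The texts still disagree on whether a hold comes first and whether resumption is open, so incompatible is the accurate word.

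**Investigators have discretion.** Section 10.4 leaves further management to the investigator, with the medical monitor available. That softens the practical effect, but it does not tell a site which written instruction is compliant.

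**The number affected may be small.** A reader might take the 11.2% of tivozanib subjects with a dose reduction in the earlier Phase 3 trial (Protocol 3.6.2) and infer 0.112 × 161 ≈ 18 affected, or use the 8.5% in the Phase 2 study (Protocol 3.7.2) for 0.085 × 161 ≈ 14. The documents support neither. Both rates count subjects with a dose reduction, not those who then fail 1.0 mg/day. The Phase 3 figure also comes from a less pretreated population, about 70% without prior systemic therapy for metastatic disease. The result is therefore neither an estimate nor a reliable ceiling.

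**Tumor assessment timing hardly changes.** A reader might infer that the classification shifts the scan schedule. On treatment, scans are every 8 weeks. After treatment, the first-year interval is given as 2 months (7.1.10), 8 weeks (9.1) or the original schedule (11.1). The first-year effect is close to nil, and no weight is placed on it.

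**The correction comes late.** SAP 4.10 dates Protocol Version 4.0 to 01 October 2018 and the primary cut-off to 04 October 2018. New wording could hardly change the primary dataset. It would still matter for anyone remaining on tivozanib and for interpreting how earlier cases were recorded.

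**Conclusion.** The conflict is real: one condition, two incompatible instructions, no precedence rule, and neighbouring sections that add a third variant instead of resolving it. Its importance lies first in patient management in the tivozanib arm. Statistically it reaches one supportive PFS analysis, the withdrawal and interruption tables, the exposure measures and, for early cases only, the per-protocol set.

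A reader might infer that the primary PFS comparison is compromised. The documents do not support that, because discontinuation of drug alone does not enter the primary definition. This conclusion assumes that subjects who stop drug continue to be scanned as the protocol requires. The size remains unknown because the documents do not give the frequency of intolerance at 1.0 mg/day. No view is taken on which instruction is clinically right.

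**What to change.** Reconcile the synopsis, section 10.4.1, section 10.4.2 and Table 4 so that one instruction for intolerance of tivozanib 1.0 mg/day appears throughout. In doing so:

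- state whether 10.4.2 applies to subjects already at 1.0 mg/day;
- say how Table 4's restart instruction applies to a subject already on the lowest supplied strength;
- correct Table 4's Grade 3 cross-reference for tivozanib.

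The content of the rule is for the sponsor's clinicians.

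Notify sites of the agreed text. For cases already recorded, the SAP's planned listings of withdrawal, dose reduction and interruption due to adverse events can help identify subjects who reached this step, so that Sensitivity Analysis #3 and the action-taken tables can be read with that in mind.

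The cost is protocol wording and a clarification letter to sites. No change to sample size, the primary analysis or data collection is needed.

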10.4.2 Tivozanib Dose Interruption

Subjects with Grade 4 drug-related toxicity, or Grade 3 drug-related toxicity that is persistent despite appropriate medical care, should have their dose interrupted to allow for resolution of the toxicity. Tivozanib may be interrupted for up to 4 weeks. If a subject is able to resume treatment after interruption of \leq 4 weeks, missed doses will not be made up (ie, cycle duration will remain unchanged). If any drug-related toxicity results in interruption of $>$ 4 weeks, the subject should be discontinued from the study unless there is clear benefit from treatment, in which case the investigator must contact the medical monitor to review the subject's condition in order to resume treatment. Subjects removed from treatment for reasons other than radiological evidence of progressive disease should still be followed with regular tumor assessments (see [Section 7.2.4](#)) until disease progression is confirmed by independent radiology review or start of new treatment, and for survival thereafter.

Any modification of study drug administration, and the reason for such action, must be clearly noted on the subject's eCRF using the Adverse Events reporting page).

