10.4.4 Sorafenib Dose Interruption

Subjects with Grade 4 toxicity, or Grade 3 drug-related toxicity that is persistent despite dose reduction and appropriate medical care, should have their treatment interrupted to allow for adequate resolution of the toxicity. Sorafenib may be interrupted for up to 4 weeks. If a subject is able to resume treatment after interruption of \leq 4 weeks, missed doses will not be made up (ie, cycle duration will remain unchanged). If any drug-related toxicity results in interruption of $>$ 4 weeks, the subject should be discontinued from the study unless there is clear benefit from treatment, in which case the investigator must contact the medical monitor to review the subject's condition in order to resume treatment. Subjects removed from treatment for reasons other than radiological evidence of progressive disease should still be followed with regular tumor assessments (see [Section 7.2.4](#)) until disease progression is confirmed by an independent radiology review or start of new treatment, and for survival thereafter.

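### The synopsis, Table 4 and sections 10.4.1 to 10.4.4 conflict at four points on when study drug is interrupted, reduced, restarted or stopped for toxicity

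*Protocol*

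**What the plan says.** The synopsis has a single paragraph headed "Dose interruption (tivozanib and/or sorafenib", so one rule covers both arms. For Grade 3 it reads "Grade 3 drug-related toxicity that is persistent despite dose reduction and appropriate medical care, should have their treatment interrupted".

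The body of the protocol splits this by drug. Section 10.4.4 (sorafenib) keeps the dose-reduction condition. Section 10.4.2 (tivozanib) does not: "Grade 3 drug-related toxicity that is persistent despite appropriate medical care, should have their dose interrupted".

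At Grade 4 the synopsis and section 10.4.2 require the toxicity to be drug-related, and Table 4 as a whole is confined to drug-related events. Section 10.4.4 opens with "Subjects with Grade 4 toxicity, or Grade 3 drug-related toxicity that is persistent despite dose reduction and appropriate medical care", where the qualifier is attached to Grade 3 only.

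Table 4 tells sites, for Grade 3 events other than hypertension and skin toxicity: "Decrease dose (see Section 10.4.2 for tivozanib and Section 10.4.3 for sorafenib dose reduction guidelines". Section 10.4.2 is the tivozanib interruption section; tivozanib dose reduction is in section 10.4.1, which is what Table 4's Grade 4 row cites.

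For a subject who cannot tolerate 1.0 mg/day of tivozanib, the synopsis says that, "due to toxicities thought to be related to tivozanib, treatment should be interrupted for up to 4 weeks". Section 10.4.1 says that tivozanib dosing should be discontinued.

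Synopsis and section 10.4.1 agree that a tivozanib reduction is permanent: "Once the dose of tivozanib is reduced, it may not be re-escalated throughout the study".

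**The concern.** These are operative safety instructions, and at the points above a site gets a different answer depending on which page it opens. Because a tivozanib reduction cannot be undone, whether a subject is reduced or interrupted first can matter for the rest of that subject's treatment.

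The statistical interest lies in the comparison of exposure and tolerability. Safety and tolerability are a secondary objective (protocol section 4.2), and the trial is open-label. SAP section 4.6 reports relative dose intensity by arm. SAP section 4.8.1 tabulates the subjects with dose reductions and with dose interruptions by arm, with reasons. If the triggers differ by arm without a stated intention, part of any difference in those tables may reflect the wording of the rules and not the drugs.

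The interrupt-or-discontinue conflict also touches counts of treatment withdrawal, and SAP Sensitivity Analysis #3, which treats stopping therapy as a PFS event.

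**Working it through.** No alpha, power, effect size or event count enters this point, so there is no formula to apply and no plan figure to reproduce. The check is to set the rules side by side. Table 4 excludes hypertension and skin toxicity, so the comparison concerns other toxicities.

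| Situation | Synopsis | Table 4 | Sections 10.4.1 to 10.4.4 |
|---|---|---|---|
| Grade 3, drug-related, tivozanib | Reduction allowed; interrupt if persistent after reduction and care | Lower the dose; no interruption step | 10.4.1: reduction allowed. 10.4.2: interrupt if persistent after care |
| Grade 3, drug-related, sorafenib | Same interruption rule | Lower the dose; no interruption step | 10.4.3: modification allowed. 10.4.4: interrupt if persistent after reduction and care |
| Grade 4, tivozanib | Interrupt if drug-related | Interrupt if drug-related; restart lower at Grade 2 or below | 10.4.2: interrupt if drug-related; no restart dose or grade |
| Grade 4, sorafenib | Interrupt if drug-related | Same as for tivozanib | 10.4.4: interrupt, relatedness not required; no restart dose or grade |
| Tivozanib 1.0 mg/day not tolerated | Interrupt for up to 4 weeks | Not addressed | 10.4.1: discontinue |

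**Grade 3.** Take a subject on tivozanib 1.5 mg/day with a drug-related Grade 3 event that persists despite medical care, and no reduction so far. Table 4 lowers the dose. The synopsis permits a reduction, and its interruption trigger is not yet met. Section 10.4.2's trigger is met, and that section states no dose or grade for resuming. On sorafenib, the equivalent subject does not yet meet the trigger in section 10.4.4. So 10.4.2 is the outlier, both against the synopsis for the same drug and against the other arm.

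**Grade 4.** The first action is the same everywhere: interrupt. Two things differ. First, relatedness: an unrelated Grade 4 event meets the sorafenib trigger in 10.4.4, but not the synopsis trigger for sorafenib, and not the tivozanib trigger in any text. Second, restart: Table 4 gives a dose direction and a grade. The synopsis, 10.4.2 and 10.4.4 say only that treatment may resume if the interruption lasted 4 weeks or less.

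**Cross-reference.** A site that follows Table 4's Grade 3 row for tivozanib dose reduction arrives at 10.4.2, the section whose Grade 3 trigger departs from the synopsis.

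**Intolerance of 1.0 mg/day.** Interruption for up to 4 weeks leaves open a return to treatment, and discontinuation ends it. Both cannot be the instruction for the same subject.

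**The case against.** The best defence is that the disagreement is narrow and the protocol leaves room for judgment. On the Grade 3 sequence, the synopsis, Table 4 and section 10.4.4 are compatible with one another. Section 10.4.1, directly before 10.4.2, allows reduction at Grade 3 or above, and 10.4.2 does not forbid it. Table 4 is headed as guidelines, and section 10.4 gives clinical judgment a role in any adverse event, so an unrelated Grade 4 event could be interrupted in either arm. Modifications and their reasons go on the eCRF (sections 10.4.1 to 10.4.3), and the SAP tables of them are descriptive.

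Much of this stands, and it limits the point. It does not remove it: discretion over further management does not explain why one rule has two wordings for the same drug, or say which governs. It cannot reconcile interrupting with discontinuing.

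Three stronger readings are tempting but unsupported:

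- A reader might infer that the order of reducing and interrupting also differs at Grade 4. It does not; no text puts reduction ahead of interruption there.
- A reader might infer that the two Grade 3 rules produce a fixed gap in tivozanib dose, 1.5 against 1.0 mg/day, for all later cycles. That needs a restart at 1.5 mg/day after interruption, which no text states. Nor does the synopsis require reduction; it only allows it.
- A reader might use the TIVO-1 rates of Grade 3 or higher events in protocol section 3.6.2 to count affected subjects. Those rates are any-cause and include hypertension and hand-foot syndrome, which Table 4 excludes. About 70% of TIVO-1 patients had no prior systemic therapy for metastatic disease, whereas this trial enrols after 2 or 3 failed regimens.

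**Conclusion.** The point holds as a set of four specific contradictions: the Grade 3 interruption trigger for tivozanib; the Grade 4 relatedness condition for sorafenib, together with a restart rule found only in Table 4; the Grade 3 cross-reference in Table 4; and interrupt versus discontinue when 1.0 mg/day is not tolerated. It is not a general disagreement among all the sections.

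The consequence is that the same toxicity can, not must, be handled differently by section and by arm. The size cannot be given: the documents do not say how many subjects would fall in the affected situations, or which text sites followed. The stake is clear safety instructions and interpretable exposure and tolerability tables. Nothing in the documents shows an effect on the primary test, which compares PFS by independent review in the ITT population. Arm differences stated alike in the synopsis and the body, such as the dose levels and sorafenib re-escalation, are not part of the problem. This should be corrected, but it does not threaten the main conclusion of the trial.

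**What to change.** Reconcile the synopsis, Table 4 and sections 10.4.1 to 10.4.4 so that each trigger, sequence and restart condition reads the same wherever it appears. That includes whether relatedness applies at Grade 4, and what follows when 1.0 mg/day is not tolerated. Where the two drugs are meant to differ, say so explicitly. Point Table 4's Grade 3 tivozanib reference at the dose-reduction section. In the same pass, correct the references to section 10.2 for skin toxicity in Table 4 and section 10.4.3; that material is in section 10.3. The clinical team decides which rule stands.

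The cost is a protocol clarification or administrative amendment and a site memo, with no new data or patients. SAP section 4.10 dates protocol Version 4.0 to 01 October 2018, three days before the cut-off of 04 October 2018, so new wording may come too late for most subjects. The study report should therefore also state, beside the tables from SAP sections 4.6 and 4.8.1, which instructions sites worked under, so that arm differences in reductions and interruptions are read with that in mind.
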